5.1.1. Subject Inclusion Criteria

In order to be eligible to participate in this study, a subject must meet all of the following criteria:

Provide signed and dated informed consent form

Female, at least 18 years of age

Reporting post-mastectomy pain at least six months removed from mastectomy or partial mastectomy (lumpectomy).

Willing to comply with all study procedures and be available for the duration of the study

Fluent in English

Women of reproductive potential must use highly effective contraception (specify methods of contraception acceptable for the study, e.g., licensed hormonal methods) and/or willingness to

undergo a pregnancy test.

5.1.2. Subject Exclusion Criteria

A potential subject who meets any of the following criteria will be excluded from participation in this study:

Previous surgical management for chronic post-mastectomy pain

Signs/symptoms which are not suggestive of neuropathic pain based on physical exam at time of consultation. See 4.2.4 above.

Pregnancy or lactation

Men will not be enrolled in this study due to the low prevalence of male mastectomy.

Anything that, in the opinion of the investigator, would place the subject at increased risk or preclude the subject's full compliance with or completion of the study.

5.3. Strategies for Recruitment and Retention

Study investigators feel that thorough training and orientation about the study will help to ensure that patient enrollment runs efficiently. All clinic staff will be briefed and updated as necessary on the study's purpose and timeline. The site coordinator will screen clinic schedules for eligible patients weekly and be prepared to meet with eligible candidates immediately following the surgical consultation, thereby reducing the time spent on study activities for patients. The study team will also use telephone and mailing strategies to increase enrollment success.

To maximize retention in the study, the site coordinator will perform all appointment scheduling for patients and integrate data collection events with the clinic schedule to avoid additional clinic trips. Additionally, to maximize efficiency and make best use of patient time, questionnaires will be offered in both electronic form (via a computer) and in hard copy.

5.4. Reasons for Withdrawal

A study subject will be discontinued from participation in the study if:

Any clinical adverse event (AE), laboratory abnormality, intercurrent illness, or other medical condition or situation occurs such that continued participation in the study would not be in the best interest of the subject.

Subjects are free to withdraw from participation in the study at any time upon request.

6. Study Schedule

6.1. Study Timeline: The proposed pilot study will run for two years and include three phases: 1) Study initiation; 2) Enrollment and initial data collection; 3) Patient follow-up and final data collection. Investigators plan on beginning in advance of grant funding, so total study time is estimated to be three years. Details of the three phases are provided below.

Phase 1- Study Initiation Month 0-1	Phase 2 – Enrollment and Initial Data Collection Months 1-12	Phase 3 – Patient Follow-up and Final Data Collection Months 13-24
--	--	--

Phase 1: Month 1 involves study training and set-up. Note: Personnel and IRB approval will be in place

prior to Month 1 so Phase 2 (enrollment) will begin as soon as possible.

Phase 2: Months 1-12 of the study will be dedicated to the enrollment and initial follow-up of the RPNI study subjects. All enrollment of subjects will be completed by Month 12 to allow for a complete follow-up period for all patients including an approximate 3 month preoperative and 9 month postoperative period. Additionally, periodic process evaluation and data auditing will occur to assure adherence to study protocol, timeline and sample size goals. Initial data analysis will take place at this time, including descriptive statistics for the study population.

Phase 3: Months 13-24 of the study will involve the conclusion of follow-up data collection for study patients and RPNI surgery for patients enrolled during months 9-12. Data will be reviewed for completeness and cleaned for analysis by the study's biostatistician. Dissemination of study findings will begin during this phase.

Final analyses, report generation, and manuscript submission will take place in the 3-6 months following completion of the funded study during a no-cost extension period.

6.2. Schedule of Events for Enrolled Patients

	Time 1	Time 2	Time 3	Time 4
	Baseline Visit	Preop Visit	3 Months Post Visit	9 Months Post Visit
PRO's	X	X	X	X
Pain Measures	X	X	X	X
CDL	X	X	X	X
Med Log	X	X	X	X
Physical Exam	X	X	X	X
Ultrasound*	X			X

* results recorded from routine diagnostic care

Time 1 – Baseline

Enrollment: Immediately following the initial consultation, the site coordinator will be available to meet with patients to describe the study. If in-person enrollment is not possible, the site coordinator will contact the patient via telephone and if interested mail a study packet with consent documents to the patient-provided mailing address. The coordinator will provide a full description of the study, answer questions, and obtain written informed consent in accordance with the IRB-approved protocol. Each patient will follow their standard non-surgical treatment plan of NSAIDs, neuropathic analgesics, opioids, and physical therapy until the surgery, estimated to be about three months.

Patient Reported Outcomes (PRO's): Patients will be asked to complete the study's initial panel of questionnaires including a demographic survey, questions about pain experience, anxiety and depression.

Medication Log: Each patient will complete a medication log (integrated with the PRO surveys) to record all medications currently being used. See Appendix B for log.

Clinical Data Log: The site coordinator will also collect key clinical data such as date of mastectomy, previous pain management therapy, ultrasound results and comorbidities. These data will be captured through the University's electronic medical records system and entered into the study's database.

Time 2 - Preoperative

Patient Reported Outcomes (PRO's): Preoperatively, patients will be asked to complete the study's panel of questionnaires describing self-reported pain experience, anxiety and depression and socio-demographic characteristics.

Medication Log: Each patient will complete a medication log (integrated with the PRO surveys) to record all medications currently being used. See Appendix B for log.

Clinical Data Log: The site coordinator will also collect additional clinical data such as changes in health history, ultrasound results and details of the pre-operative pain management. These data will be captured through the University's electronic medical records system and entered into the study's database.

Time 3 – Three Months Post-Surgery

Patients will be scheduled for a 3-month post-surgical visit at the peripheral nerve clinic. During this visit, the following data will be collected.

Patient Reported Outcomes (PRO's): Patients will be asked to complete the study's panel of questionnaires describing self-reported pain experience, anxiety and depression.

Medication Log: Each patient will complete a medication log (integrated with the PRO surveys) to record all medications currently being used. See Appendix B for log.

Clinical Data Log: The site coordinator will also collect additional clinical data such as changes in health history, ultrasound results, surgical detail, and surgical complications. These data will be captured through the University's electronic medical records system and entered into the study's database.

Time 4 – Nine Months Post-Surgery

Patients will be scheduled for a 9-month post-surgical visit at the peripheral nerve clinic. During this visit, the following data will be collected.

Patient Reported Outcomes (PRO's): Patients will be asked to complete the study's panel of questionnaires describing self-reported pain experience, anxiety and depression and socio-demographic characteristics.

Medication Log: Each patient will complete a medication log to record all medications currently being used. See Appendix B for log.

Clinical Data Log: The site coordinator will also collect additional clinical data such as changes in health history, ultrasound results, complications and details of the post-operative pain management regimen. These data will be captured through the University's electronic medical records system and entered into the study's database.

7. Assessment of Safety

7.1. Adverse Events

There is minimal perceived risk associated with this study. The PI and study team will appropriately manage any adverse outcomes, psychological or otherwise, and report them to the IRB per institutional guidelines.

7.2. Unanticipated Problems

The Office for Human Research Protections (OHRP) considers unanticipated problems involving risks to subjects or others to include, in general, any incident, experience, or outcome that meets **all** of the following criteria:

unexpected (in terms of nature, severity, or frequency) given (a) the research procedures that are described in the protocol-related documents, such as the IRB-approved research protocol and informed consent document; and (b) the characteristics of the subject population being studied;

related or possibly related to participation in the research (in the guidance document, possibly related means there is a reasonable possibility that the incident, experience, or outcome may have been caused by the procedures involved in the research); and

suggests that the research places subjects or others at a greater risk of harm (including physical, psychological, economic, or social harm) than was previously known or recognized.

An incident, experience, or outcome that meets the three criteria above generally will warrant consideration of substantive changes in order to protect the safety, welfare, or rights of subjects or others. Examples of corrective actions or substantive changes that might need to be considered in response to an unanticipated problem include:

changes to the research protocol initiated by the investigator prior to obtaining IRB approval to eliminate apparent immediate hazards to subjects

modification of inclusion or exclusion criteria to mitigate the newly identified risks

implementation of additional procedures for monitoring subjects

suspension of enrollment of new subjects

suspension of research procedures in currently enrolled subjects

modification of informed consent documents to include a description of newly recognized risks

provision of additional information about newly recognized risks to previously enrolled subjects.

Unanticipated problems will be recorded and reported throughout the study.

7.3 Safety Oversight

The RPNI study will have a Data Safety and Monitoring Plan to oversee data security and adherence to study protocols. The study principal investigator, [name] will be ultimately responsible for ensuring proper data procedures and security. In addition, a Data Safety and Monitoring Committee, headed by [name]. [name], Section Chief of Plastic Surgery at the University of Michigan will also oversee the safety of the data processes and convene if necessary.

8. Statistical Considerations

Twenty-five patients will be enrolled into the study (~50% of patients seen in the Multidisciplinary Peripheral Nerve Clinic with post-mastectomy pain in a single year), and of them we expect 23 patients to choose to undergo RPNI surgery (over 90% of the expected enrollment number). Assuming about 10% non-response

or dropout rate, the expected sample size of 20 patients receiving RPNI is expected to give 80% power to detect a mean improvement in post-operative outcome between T1 and T4 (including the primary outcome of pain) of 1.11 standard deviation (SD) or larger using a 0.05 level two-sided test. From our preliminary data based on limb amputations, we expect the pain reduction to be at least 6 points for neuroma pain with an SD of the change of about 1.8 points, which corresponds to a minimum change of 3.3 SD (= 6/1.8). Hence the proposed sample size is expected to give more than adequate power to detect a clinically meaningful level of improvement. For the outcome of opioid use, the proposed sample size is expected to have 83% power using McNemar's test to detect a reduction in opioid use from 78% prior to RPNI to 22% after RPNI at 9 months.

Data will be collected longitudinally to assess trends in patient reported outcome (PRO) measures over time (Aim 1). We will assess the distribution of all PRO measures for skewness or outlying values and report summary descriptive statistics at baseline and postop time points for each measure. The extent of non-response at each timepoint will be assessed and reported as a variable of interest. Data will be visualized graphically to see if the reduction in pain occurs gradually or if all pain reduction is complete by a specific time but maintained afterwards. We will model the longitudinally collected follow-up outcomes data using mixed-effects regression models with baseline values of the selected outcome measure and follow-up time as predictors. Using the regression model, we will look for potential predictors of variation in follow-up outcomes. Covariates such as age, race and ethnicity will be examined.

To assess if RPNI surgery results in durable protection from neuroma recurrence (Aim 2), we will monitor physical exam findings at each of the RPNI sites including Tinel sign or evidence of altered sensation in the corresponding dermatome. The initial evaluation at the time of enrollment will provide a baseline of the number of altered sensation categories the patient experiences (shooting pain, burning pain, or tingling). Ultrasound will provide baseline information regarding presence/absence of neuroma, and size of the neuroma. We expect the changes to be in the direction of improvement, but two-sided tests will be used to evaluate 1) presence or absence of any altered sensation physical exam finding, 2) number of altered sensation physical exam findings, 3) presence or absence of ultrasound evidence of neuroma, 4) size of neuroma (if present). As the data will be collected longitudinally at multiple follow-up visits (3 and 9 months postop), we will assess trends in these outcome measures over time.

9. Source Documents and Access to Source Data/Documents

Each participating site will maintain appropriate medical and research records for this trial, in compliance with ICH E6, Section 4.9 and regulatory and institutional requirements for the protection of confidentiality of subjects. Describe who will have access to records.

Source data will originate from medical records of clinical findings (MiChart), observations, and patient completed surveys.

10. Quality Control and Quality Assurance

A User's Manual containing the study's standard operating procedures (SOPs) for quality management will be developed and will include:

How data will be evaluated for compliance with the protocol and for accuracy in relation to source documents.

The documents to be reviewed (e.g., CRFs, clinic notes, product accountability), who is responsible, and the frequency for reviews. Methods of training for staff, and methods of tracking such training.

11. Ethics/Protection of Human Subjects

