ID: UMCC 2018.124

Surgical Treatment of Post-surgical Mastectomy Pain Utilizing the Regenerative Peripheral Nerve Interface

NCT04530526

**Surgical treatment of post-surgical mastectomy pain utilizing the
regenerative peripheral nerve interface (RPNI)**

PROTOCOL SUMMARY

Title:	Surgical treatment of post-surgical mastectomy pain utilizing the regenerative peripheral nerve interface (RPNI)
Summary:	Up to 40% of patients who undergo mastectomy suffer from chronic pain, defined as pain lasting greater than three months. Chronic post-mastectomy pain due to nerve injury leads to long-term opioid use and diminished quality-of-life. A novel surgical approach to neuroma treatment, the regenerative peripheral nerve interface (RPNI) developed to treat painful neuromas associated with limb amputation has shown significant reductions in patient-reported pain. RPNI surgery is now available through Michigan Medicine's Multi-Disciplinary Peripheral Nerve (MDPN) Clinic to improve post-mastectomy pain and definitively treat intercostal neuromas following mastectomy. Using patient-reported outcomes and clinical data we will evaluate the use of RPNI surgery to reduce persistent post-mastectomy pain in women seeking surgical consultation through the Plastic Surgery or MDPN clinics.
Objectives:	Our central hypothesis is that intercostal nerve RPNI surgery significantly reduces chronic post-mastectomy pain without neuroma recurrence. We will employ an observational study design with patients serving as their own controls prior to surgery to assess pain levels before and after RPNI surgery for intercostal neuroma.
Population:	Adult female patients (≥ 18 years old) presenting to Michigan Medicine's MDPN Clinic with post-mastectomy pain persisting at least six months removed from mastectomy will be eligible for participation.
Number of Sites:	Single Center - University of Michigan
Study Duration:	Two years (NIH funded). Three years total.
Subject Participation Duration:	Approx. 12 months.
Description of Intervention:	Survey based patient reported outcomes from patients undergoing RPNI surgery, clinical data collection
Enrollment Period:	12 months
Estimated Sample Size:	25 patients

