The central hypothesis for this study is that intercostal RPNI surgery significantly reduces chronic post-mastectomy pain with absence of painful neuroma recurrence.

Aim 1: To examine the use of RPNI surgery to reduce post-mastectomy pain and opioid consumption.

We will obtain patient-reported outcomes (PRO's), using previously validated tools, to examine the effect of RPNI surgery on post-mastectomy pain and opioid use. Patients who are at least six months removed from mastectomy and exhibit clinical signs and symptoms of neuropathic pain will be asked to enroll in this IRB-approved study. Patients will be excluded if mastectomy occurred less than six months prior or if they have had previous surgical interventions to treat pain. Upon completion of Aim 1, we will assess the association between intercostal RPNI surgery and neuropathic pain in post-mastectomy patients.

Aim 2: To demonstrate absence of neuroma recurrence in post-mastectomy patients after intercostal RPNI surgery.

Neuroma recurrence in patients treated with intercostal RPNI will be evaluated using physical exam findings and ultrasound (14, 17-20). Patients will be assessed immediately following enrollment, preoperatively, and at subsequent intervals (3 and 9 months) following RPNI. Upon completion of Aim 2, we will demonstrate that intercostal RPNI surgery provides durable relief from neuroma recurrence.

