2.4.2. Known Potential Benefits

The prescribing of opioid medications to treat pain, including chronic pain following surgery, has become a critical issue across the U.S. Reports indicate that 10% of opioid naïve patients who undergo mastectomy require opioids for pain relief at least three months after surgery and up to 40% of patients who undergo mastectomy report post-surgical pain lasting greater than three months. Three years after surgery, nearly 25% of patients continue to report moderate persistent pain after the mastectomy procedure which involves the transection of small sensory nerves present and traveling through excised breast tissues. This study is a novel approach to improving post-mastectomy quality of life and reducing dependence on pain medications and the ensuing risk of dependence and addiction.

3. Hypotheses and Objectives

Aim 1: To examine the use of RPNI surgery to reduce post-mastectomy pain and opioid consumption.

3.1. Hypothesis: Neuroma resection and RPNI surgery to treat intercostal neuromas will reduce patient-reported post-mastectomy pain, depression/anxiety scores, and opioid use to a greater degree than will conservative neuropathic pain management.

3.1.2. Objective: Identify patients with post-mastectomy pain who have been referred to the Multi-Disciplinary Peripheral Nerve (MDPN) or Plastic Surgery Clinics and evaluate their neuropathic pain, depression and anxiety levels, and opioid use pre- and post-treatment.

We will enroll patients seeking surgical treatment for chronic post-mastectomy pain upon referral to our institutional Multi-Disciplinary Peripheral Nerve Pain (MDPN) Clinic or Plastic Surgery. The presence of neuropathic pain will be evaluated by the combined efforts of plastic surgeons, peripheral nerve surgeons, anesthesia pain providers, and physiatrists. Each patient's medication usage will be logged at pre- and post-surgical timepoints.

Aim 2: To demonstrate absence of neuroma recurrence in post-mastectomy patients after intercostal RPNI surgery.

3.2. Hypothesis: Intercostal nerves treated with RPNI will remain free of neuroma recurrence through nine months after RPNI surgery.

3.2.2. Objectives: Evaluate patient reported outcomes of intercostal RPNI surgery and clinical indicators such as routine ultrasound review and physical exam.

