3.3. Study Outcome Measures

Upon successful execution of **Aim 1**, we will demonstrate that:

- 1) RPNI surgery improves patient-reported physical and psychosocial well-being (patient reported depression and anxiety) within three months after surgery.
- 2) Patients who undergo RPNI surgery will report reduced daily opioid consumption within 3 months after surgery.

Upon successful execution of **Aim 2**, we will demonstrate that:

- 1) RPNI surgery provides long-term protection from neuroma recurrence based on physical exam and ultrasound.

4. Study Design

4.1. Methodology: Patients seeking surgical consultation for RPNI surgery in the Multidisciplinary Peripheral Nerve Clinic for chronic post-mastectomy pain will be recruited for this study and followed longitudinally at four time points to evaluate pain, medication usage, anxiety and depression reporting compared to preoperative levels.

Upon enrollment, patients will complete baseline questionnaires including a self-reported medication log (Time 1) and continue their standard non-surgical management plan while awaiting surgery. As an elective surgery, patients' scheduled surgery dates usually occur approximately 3 months after initial consultation. Note: although investigators expect some variability on surgery scheduling, the average time of study involvement for each patient will be 12 months. This represents approximately three months before surgery and nine months after surgery.

Approximately two weeks prior to surgery (during the patient's scheduled preoperative visit), participants will complete the panel of surveys, including medication log (Time 2) and again following RPNI implantation at three (Time 3) and nine months (Time 4) post procedure. The validated PRO instruments will be used to evaluate patients' reported pain experiences, depression, and anxiety (see below). The medication logs will document the details of each patient's medication use over time (see Appendix B Patient Medication log). Study duration will allow patients enrolled during the first 12 months to be followed for the entire study duration.

Presence of neuropathic pain will be confirmed based on detailed history, physical exam findings (e.g. Tinel sign or pins/needles, burning, or shock-like sensations) and local anesthetic nerve blocks which are all part of routine assessment and evaluation at the clinic.

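### The pain outcome is powered on enrolment (T1) to nine months (T4), so about 2.5 months of non-surgical waiting is counted with surgery; the preoperative T2 panel has no role in any outcome test, and hypothesis 3.1 has no test

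*Combined protocol and SAP*

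**What the plan says.** **Visits.** Sections 4.1 and 6.2 set four visits: T1 at enrolment, T2 about two weeks before surgery, T3 and T4 at three and nine months after it. Surgery usually falls about three months after the first consultation, and non-surgical treatment continues until then. The survey panel and medication log are completed at all four visits. Both sections label T1 as baseline.

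**Pain contrast.** The only pair of visits that Section 8 names for pain is in the power statement: a "mean improvement in post-operative outcome between T1 and T4 (including the primary outcome of pain".

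**Aim 1 analysis.** Section 8 plans "mixed-effects regression models with baseline values of the selected outcome measure and follow-up time as predictors" and will "report summary descriptive statistics at baseline and postop time points for each measure". Given the labels in 4.1 and 6.2, baseline here means T1.

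**Wording that fits T1 or T2.** Section 4.1 says the study will "evaluate pain, medication usage, anxiety and depression reporting compared to preoperative levels". The McNemar power statement for opioid use refers only to the time before RPNI. Neither names a visit.

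**Design and claim.** The Protocol Summary describes "patients serving as their own controls prior to surgery to assess pain levels before and after RPNI surgery". Hypothesis 3.1 says RPNI will reduce pain, depression/anxiety scores and opioid use "to a greater degree than will conservative neuropathic pain management". The Aim 1 statement that closes Section 2.3 is more modest: "we will assess the association between intercostal RPNI surgery and neuropathic pain in post-mastectomy patients". Of 25 enrolled, Section 8 says "we expect 23 patients to choose to undergo RPNI surgery".

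**The concern.** The T1-T4 change is the sum of two parts: T1-T2, on non-surgical care, and T2-T4, which spans surgery. Only the second can reflect RPNI. Patients may enrol when their pain is at its worst, or their medication may be adjusted while they wait. If so they may improve before surgery, and T1-T4 overstates the change after it. If they worsen while waiting, T1-T4 understates it. T2 is the visit that separates the two parts, yet no outcome test uses it.

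Hypothesis 3.1 is a separate matter and does not depend on any drift. It makes a comparative claim. The plan has no concurrent control arm, only about 25 - 23 = 2 enrolled patients are expected to forgo surgery, and no stated analysis sets change on conservative care against change after RPNI.

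The protocol intends the results as preliminary data for a multi-institutional trial (Section 2.3), so a biased estimate of change would carry into the planning of that trial.

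**Working it through.** **Inputs from Section 8:** n = 20; two-sided 0.05; SD of change 1.8 points; expected reduction 6 points; printed detectable change 1.11 SD. **From 4.1:** T1-T2 is about 3 months less 2 weeks, or 2.5 months; T2-T3 about 3.5 months; T2-T4 about 9.5 months. **Assumed, because the documents give none:** the waiting-period change w, in SDs of a single score; within-patient correlation rho of 0.5 or 0.7, equal between all visits (compound symmetry); a paired t-test.

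**1. The plan's own figures.** 6/1.8 = 3.3 SD is reproduced. The 1.11 SD is not: a paired t-test with n = 20 detects 0.66 SD of change at 80% power, and its power at 1.11 SD is 99.7%. The printed figure errs on the cautious side and nothing below depends on it.

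**2. No surgical effect, improvement w before T2 only.** SD of change = sqrt(2(1 - rho)) score SDs, which is 1.000 at rho 0.5 and 0.775 at rho 0.7. At an SD of change of 1.8 points, the score SD is 1.8/1.000 = 1.80 or 1.8/0.775 = 2.32 points. Bias = w × score SD. The noncentrality is (w / SD of change) × sqrt(20).

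| w | rho | Bias (points) | Share of 6 points | T1-T4 significant |
|---|---|---|---|---|
| 0.2 | 0.5 | 0.36 | 6% | 14% |
| 0.3 | 0.5 | 0.54 | 9% | 25% |
| 0.5 | 0.5 | 0.90 | 15% | 56% |
| 0.2 | 0.7 | 0.46 | 8% | 20% |
| 0.3 | 0.7 | 0.70 | 12% | 38% |
| 0.5 | 0.7 | 1.16 | 19% | 78% |

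Under the same conditions T2-T4 stays at 5%.

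**3. Worsening by the same amounts.** At a true T2-T4 effect of 1.11 SD (2.0 points), T1-T4 power is 97, 93 and 73% (rho 0.5) or 95, 87 and 50% (rho 0.7), against 99.7% from T2. At 3 points it is 99% or more throughout, and at 6 points about 100%.

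**4. What T2 anchoring cannot remove.** Suppose an improvement of 0.04 score SD per month runs on to T4 with no surgical effect. T1-T4 collects 12 × 0.04 = 0.48 SD and is significant in 53% / 75% of trials (rho 0.5 / 0.7). T2-T4 collects 9.5 × 0.04 = 0.38 SD and is still significant in 36% / 55%.

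**5. Own-control contrast for 3.1:** (T4 - T2) - (T2 - T1). Under compound symmetry its SD is sqrt(3) times that of a simple change, or 1.8 × 1.732 = 3.12 points. With n = 20, an effect of 2 points is 2/3.12 = 0.64 SD (power about 78%) and 3 points is 3/3.12 = 0.96 SD (about 98%). Under the drift in step 4 it is significant in about 11% / 14%, because its intervals are unequal.

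**6. Precision of the T1-T2 change.** The 95% half-width is t(0.975, n - 1)/sqrt(n): 0.47 SD at n = 20 (0.84 points) and 0.41 SD at n = 25 (0.74 points). This can show a drift of about 1 point but not a small one.

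**The case against.** **T1-T4 appears only in the power statement.** The analysis text specifies a mixed model with the baseline value as a covariate and names no paired t-test. This stands. The rejection rates above illustrate a T1-T4 paired test and are not error rates of the specified model. But T1-T4 is the only contrast named for pain, and nothing in Section 8 substitutes T2.

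**Baseline is defined.** It is: 4.1 and 6.2 both give it as T1. A reader might infer that the model's baseline is left open, and the documents do not support that. The clear label confirms that the waiting period falls inside the contrast. What stays open is which visit the preoperative comparison in 4.1 and the opioid test use.

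**T2 is not excluded.** Graphs and trend summaries could show all four visits. That is fair, but a graph does not fix the reference visit for the main result.

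**The drift is hypothetical and the planned effect is large.** Both are true. No document gives a waiting-period change, and at 6 points the conclusion would not alter. However, the 6 points come from limb-amputation data, and bias in the estimate remains even when significance is assured.

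**The study can address 3.1.** A reader might infer that, without a control arm, it cannot. That goes too far: patients are described as their own controls before surgery, and T1-T2 is a period on conservative care. What is missing is a stated test that uses it.

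**Conclusion.** The point holds. Section 8 powers pain on T1 to T4, T1 is enrolment, and about 2.5 months of non-surgical care lie between T1 and T2. No outcome test uses T2, and no stated test examines the comparative clause of 3.1.

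The size is unknown. Under the assumed improvements of 0.2 to 0.5 SD the bias is 0.36 to 1.16 points, or 6-19% of the planned 6 points. The main harm is a biased estimate. Lost power matters only if patients worsen while waiting and the true effect is about 2 points or less. A reader might take the 14-78% as the plan's false-positive rate. The documents do not support that, because those figures need both an assumed drift and a test that the analysis text does not name.

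This should be fixed before analysis, so that the choice between T1 and T2 is not made after the data are seen.

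**What to change.** 1. In Sections 8 and 4.1, make T2 the preoperative reference: for the main pain contrast (T2-T4), for the preoperative comparison in 4.1 and for the McNemar test. Use T2 as the baseline covariate in the mixed model. Keep T1-T4 as secondary.
2. Report the T1-T2 change with its 95% CI beside the T2-T3 and T2-T4 changes.
3. For hypothesis 3.1, do one of two things. Either specify the own-control contrast (post-surgery change minus waiting-period change) as its test, and state that it has no concurrent control and that its intervals are unequal; T2-T3, about 3.5 months, matches the 2.5-month wait more closely than T2-T4. Or reword 3.1 as a before-after claim, in line with the association wording under Aim 1 in Section 2.3.
4. State that anchoring on T2 removes waiting-period change only, not drift after T2.

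**Cost.** Wording and a little more analysis. T2 already collects the panel and the medication log, and the detectable change stays at 0.66 SD with n = 20 if the SDs of change from T1 and T2 are similar. The own-control contrast has a wider interval: its SD is larger by sqrt(3), so its 95% half-width at n = 20 is 0.468 × 1.8 × 1.732 = 1.46 points, against 0.84 for a simple change.
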